## **ABBREVIATIONS/DEFINITIONS**

- African-American (AfAm)
- Data Safety and Monitoring Board (DSMB)
- National Institutes of Health (NIH)
- Physical Activity (PA)
- Principal Investigator (PI)
- Randomized Controlled Trial (RCT)

## 1.0 Objectives

### 1.1 Purpose:

The primary objective of this study is to test the feasibility, acceptability, safety and targeted outcomes of a 3-month hatha and restorative yoga intervention to decrease sedentary behavior (primary outcome), stress and blood pressure in 60 sedentary (<30 minutes of moderate-to-vigorous PA per week) African-American women. The proposed study has four aims:

Aim 1: To refine a promising and innovative intervention to enhance its feasibility. Based on our previously developed intervention, I HEART Yoga!, and subsequent experience, we will refine intervention strategies to incorporate findings from the pilot research and theoretically ground the intervention using an integrated model incorporating constructs from the Social Cognitive Theory and collectivism (i.e., social connectedness, sense of belonging, and community cohesion). We will conduct two focus groups of sedentary African-American women (n=16) to seek feedback on the intervention strategies (e.g., yoga sequences).

Aim 2: Assess feasibility of a hatha and restorative yoga intervention (n=30) compared to a control group (n=30). We will examine feasibility of participant recruitment, retention and adherence; fidelity of intervention delivery; and intervention materials.

Aim 3: Evaluate the acceptability and safety of a hatha and restorative yoga intervention (n=30) compared to a control group (n=30). We will examine the acceptability of intervention location and strategies, class format, enjoyment of sessions, and safety of the intervention.

Aim 4: To test feasibility and appropriateness of the targeted outcomes (i.e., primary: sedentary behavior and secondary: blood pressure and stress) for subsequent trials. It is important to properly measure expected outcomes but not make comparisons between intervention and control groups.

## 2.0 Background

### 2.1 Significance of Research Question/Purpose:

A sedentary lifestyle is associated with chronic cardiovascular and physiological diseases and psychological disorders. Indeed, the 2018 Physical Activity Guidelines for Americans emphasize targeting sedentary time (i.e., waking behaviors in a seated or reclining posture at low energy expenditure), independent of total activity. The Guidelines state: "Adults should move more and sit less throughout the day. Some physical activity is better than none." The U.S. has now joined at least six other countries in adopting guidelines to reduce sedentary time. Persuasive evidence has emerged in the last 10 years: (a) adults spend inordinate time sedentary (~7.5 hr/day on average); (b) physiological mechanisms linking sedentary time to increased chronic disease risk are understood, and (c) excess mortality due to sedentary behavior is substantial. The current Guidelines are calling for evidence-based interventions to reduce sedentary time. For African-American women who disproportionately have sedentary lifestyles, a "move more and sit less" philosophy to target decreasing sedentary behavior is appropriate. Sedentary lifestyle has contributed to African-American women being 80% more likely to be overweight or obesity compared to non-Hispanic white women, and

suffering from high rates of heart disease, hypertension, and other conditions. These statistics present a significant public health problem that must be addressed. Decreasing sedentary time has many mental, social, and psychological health benefits. Given the current state of health statistics among African-American women, it remains critical to find innovative ways to decrease sedentary time in this population.

## **2.2 Preliminary Data:**

Co-PI [name] conducted a 6-month, randomized controlled, pilot yoga intervention, *I HEART Yoga!*, with 59 overweight, sedentary African-American women. Thirty women were randomized to the intervention group and offered in-person and online yoga classes; the 29 women in the usual care, control group received a 3-month membership at a local yoga studio after post-intervention data collection was completed. The aim of this pilot was to engage participants in yoga at least 3 times per week and to examine the effects on blood pressure, stress, and physical activity. A post-intervention focus group revealed that participants enjoyed the intervention and posted several affirmations on a private Facebook group page. Although the feedback was positive, there were several areas of *I HEART Yoga!* pilot study that participants recommended improving and enhancing, thus warranting the proposed *YogaMoves* feasibility study to test refined strategies.

## **2.3 Existing Literature:**

**Previous interventions to decrease sedentary behavior in African-American women.** Previous interventions for African-American women to address sedentary lifestyles have mainly included traditional physical activity strategies such as walking, aerobics and dance. Walking programs, the most utilized of the interventions, are easy to implement, require minimum equipment, and usually are safe and acceptable for high-risk populations, such as sedentary adults carrying excess weight. However, focus groups with African-American women reported that the repetitiveness and monotony of traditional exercise interventions (i.e., walking and aerobics) may reduce motivation or cause musculoskeletal issues that may make typical, repetitive weight-bearing exercise uncomfortable or painful.

**Increasing interest of yoga to address health outcomes.** Yoga is a well-established Eastern practice that is promoted as a safe and effective way to encourage less sedentary behavior; improve strength, balance, and flexibility, and decrease depression and stress. Like walking, yoga is a minimal equipment activity, can be practiced almost anywhere at a variety of intensities, and can be used to decrease inactivity. However, yoga introduces not only physical movement, but also mindfulness and deep breathing that can lead to mental and psychological benefits, and may be as effective as higher intensity activity for improving some health-related outcomes.

**How can yoga decrease sedentary behavior?** Preliminary research suggests that there are several mechanisms proposed for yoga to lead to better health outcomes. Biological mechanisms related to the autonomic nervous system have been connected to lowering blood pressure. Stress has been positively impacted through a biological mechanism of improved circadian patterns in cortisol release, and through psychological mechanisms such as increased positive attitudes towards stress, self-awareness, coping mechanisms, appraisal of control, spirituality,

compassion, and mindfulness. Lastly, it is plausible for yoga to positively impact sedentary behavior as evidence supports that yoga aids in behavioral self-regulation.

**Yoga as a potential intervention for African-American women.** Much of the research on yoga has not focused on African-American populations despite the potential for suitability and effectiveness. Yoga research studies including African-Americans have primarily targeted those with breast cancer, heart failure, metabolic syndrome, arthritis, or low back pain. These studies found yoga to be an effective strategy or acceptable form of activity. Based on these previous studies and pilot work by our research team, yoga appears to be well-suited to engage African-American women to have less sedentary lifestyles.

In the U.S., yoga has become increasingly popular in recent years. From the 2017 National Health Interview Survey (NHIS) Adult Complementary and Alternative questionnaire, over 14 million people stated they have practiced yoga in the past year. Although yoga has the reputation of attracting college-educated, white populations and is sometimes viewed as exclusionary to those outside that community, it has become increasingly popular among African-Americans with the growth of Afrocentric yoga (i.e., focusing on Black or African culture), establishment of Black yoga organizations, and expansion of social media presence of African-American yoga practitioners. Furthermore, data from the NHIS questionnaire reported that almost 10% of African-Americans have practiced yoga in the past year compared to 13.5% of white Americans.

African-American women attend mainstream (i.e., majority white) yoga classes, but they do not always continue, partially due to unfamiliarity with various aspects of yoga. Chanting, use of Sanskrit instead of English to name poses, and “religious” sounding music can stimulate preconceived notions that yoga conflicts with religious beliefs. An additional barrier to adopting and sustaining a yoga practice is not feeling included due to the lack of representation of full-body, African-American yoga practitioners. Previous yoga studies that targeted African-Americans and modified classes to make it more culturally acceptable (i.e., no chanting, generic instrumental music, English names for poses, matching yoga instructors by race with participants), reported that participants found yoga to be more acceptable. One study even reported that 100% of the participants were still practicing yoga three months after the intervention. These culturally appropriate modifications have been critical in African-American women being open to practicing yoga and subsequently recognizing the health benefits.

In summary, the **scientific premise** of our proposed pilot study is that African-American women are highly affected by a sedentary lifestyle, and yoga is an engaging activity with biological and psychological mechanisms having promise to reduce sedentary behavior and improve health outcomes such as blood pressure and stress. The proposed study is highly significant given that it will address the need for innovative and culturally acceptable approaches to reduce sedentary time among those at elevated risk for chronic diseases.

### **3.0 Study Endpoints/Events/Outcomes**

#### **3.1 Primary Endpoint/Event/Outcome:**

This is a feasibility study, therefore the primary endpoints of interests are related to feasibility and acceptability of the intervention.

- Feasibility: Recruitment of participants - 200 women recruited and screened; 76 women (16 for Aim 1 focus groups and 60 for pilot intervention) enrolled and consented
- Feasibility: Retention and adherence -  $\geq 80\%$  of intervention participants attend  $\geq 80\%$  of intervention sessions
- Feasibility: Fidelity of intervention delivery -  $\geq 90\%$  of each videotaped session is delivered as planned based on training
- Feasibility: Intervention materials and resources - 100% of intervention materials and resources are delivered as planned
- Feasibility: Assessment measures -  $\geq 80\%$  intervention and control participants rate the assessments as not too burdensome;  $\geq 90\%$  intervention and control participants will complete baseline, post-intervention and 3-month follow-up assessments
- Acceptability: Intervention location, in-person classes, instructors, home-based resources -  $\geq 90\%$  intervention participants rate the various intervention components as acceptable
- Acceptability: Yoga intervention -  $\geq 90\%$  intervention participants rate intervention acceptable
- Safety: Adverse events - Zero severe adverse events (causes major disruption to participant's life, e.g., sprain, broken bone, CV event, death), zero moderate adverse events (causes minor inconvenience to participant, e.g., fainting spell, sore muscles for more than 3 days) and  $<10\%$  of participants report mild adverse events (no major impact, e.g., headache, sore muscles for 2-3 days)

### 3.2 Secondary Endpoint(s)/Event(s)/Outcome(s):

- Sedentary behavior
- Blood pressure
- Stress

## 4.0 Study Intervention(s)/Interaction(s)

### 4.1 Description:

Formative assessment focus groups: After the research team revises the intervention strategies, the newly revised intervention strategies, including yoga sequence, will be presented and discussed during two focus groups of 6-8 sedentary African-American women. Please note that if the focus group participants propose intervention strategies different from what is expected by the MPIs, the MPIs will submit modifications to the IRB. Due to COVID-19 restrictions, these focus groups will take place virtually approximately in April - June 2021.

Yoga intervention: Please note that although we are anticipating conducting the yoga pilot intervention in-person, it is dependent on whether it is safe to have face-to-face contact due to COVID-19. If it is deemed unsafe to have face-to-face contact, the MPIs will submit a modification to IRB to reflect this change. Additionally, if it is safe to conduct the intervention face-to-face, the MPIs will submit the University-required "Sunrise Plan" outlining risk mitigation related to COVID-19.

Participants engaged in the formative assessment focus groups may be invited to be a part of the pilot RCT. 60 participants will be randomly assigned to the yoga intervention (n=30) or control condition (n=30). It is anticipated that the yoga intervention will be a hybrid delivery (combination of in-person and virtual) (June – August 2022) at two intervention locations, 612 Jungle and The Zen Bin. There will be no contact with control participants during the implementation of the yoga intervention. The yoga intervention components are:

- Hybrid, 60-minute yoga sessions will take place three times per week for 12 weeks to include a sharing circle at the end of each session. Participants will unite in a sharing circle to provide feedback as a group on how the practice felt and strategies for integration into ones' daily life. Specifically, each session will include gentle hatha yoga which includes physical poses combined with stretching, breathing and some meditation. A proposed session would include:
  - Warm-Up: Controlled Breathing Meditation & Mindfulness (10 minutes): Mindful breathing (4-6 second inhales/exhales) through nose to increase focus on yoga practice and to build internal heat to better prepare the body for movement
  - Warm-Up: Gentle Movement (5 minutes): Child's, Cat/cow, Thread the needle, Side puppy
  - Active Movement: Strength, Flexibility & Balance Poses (20 mins):
  - Cool Down: Stretching Poses (10 mins): Cobbler's, Seated forward fold, Legs up the wall, Happy baby, Spinal twist
  - Cool Down: Resting Pose (5 mins): Final resting pose on back using props
  - Sharing Circle & Wrap-Up (10 mins): Group gathers in circle and share feedback about yoga session

These classes will be held in-person, but there will be a synchronous option for participants to join virtually. Yoga sessions will be led by certified yoga instructors from the greater Twin Cities metro area. As preparation for the pilot RCT, they will participate in intervention-specific training developed by research staff regarding (1) instructing yoga as part of a scientific study, and (2) the practice of restorative yoga for race-based trauma. They will be provided yoga sequences outlined by research staff and quality control data will be collected as described in section 15.2.

- A private Facebook group will be set up to keep participants connected to each other, thus further promoting collectivism, and for the research staff to maintain contact and share information with participants. Participants will be able to post freely to the Facebook page to stay connected, offer encouragement, and provide accountability to attend the weekly yoga sessions. Research assistants will keep track of the number of posts and "likes" each participant makes. Research staff will use Facebook to maintain contact and to share information with participants: 1) provide a weekly reminder for upcoming yoga sessions and workshops; 2) inform/remind participants of the biweekly themes of the sessions – there will be a new theme every other week (i.e., weeks 1, 3, 5, 7, 9, 11); and 3) remain accessible to participants for assistance or requested information participants may need. This contact will be virtual.

- To align with and reinforce the biweekly themes established for the weekly yoga sessions (i.e., common yoga poses, the importance of breath, strengthening your core), biweekly, hybrid workshops will be offered. These workshops will take place during weeks 2, 4, 6, 8, 10, and 12 and will be specialty classes that allow participants additional exposure to meditation and breathing and longer class formats so they can delve deeper into yogic philosophy and practice. These workshops will be held in-person, but there will be a synchronous option for participants to join virtually.

Data collection: Yoga intervention and control participants (n=60) will complete baseline (March – May 2022), post-intervention (September – October 2022), and 3-month follow-up measures (January – February 2023) in-person at the University of Minnesota’s Epidemiology Clinical Research Center.

Post-intervention focus groups: Four groups (high attendance and low attendance from each intervention location) of randomly chosen intervention participants (anticipated n~20) will be invited to participate in a post-intervention focus group to assess intervention feasibility, acceptability, and safety with the overall program and specific components, and in order to inform program improvements. Focus groups will take place at the Epidemiology Clinical Research Center.

## 5.0 Procedures Involved

### 5.1 Study Design:

Our proposed feasibility study will be two-arm, RCT with 60 participants randomly assigned to either an intervention group (n=30) or control group (n=30).

### 5.2 Study Procedures:

Formative assessment focus groups will be conducted in April - June 2021. Data collected from these focus groups will be qualitative feedback on the proposed intervention strategies. The focus group guide is submitted with this IRB application.

Data collected directly related to the pilot RCT yoga intervention will be:

- Quality control data to make sure the yoga movements follow protocol and are safe for participants will be collected during the implementation of the yoga intervention. One yoga session will be randomly selected biweekly (during weeks 2, 4, 6, 8, 10, and 12) and videotaped so the content can be analyzed based on the established criteria related to poses, breathing and meditation. During these videotaped quality control sessions, participants will be asked to wear the activPAL to assess activity intensity.
- Acceptability of yoga classes will be assessed during the yoga intervention via a short self-reported survey after each yoga session. The survey is included with this application.
- Three, in-person data collection time points: baseline (March – May 2022), post-intervention (September – October 2022), and 3-month follow-up measures (January – February 2023). Data to be collected during these time points are:
  - Sedentary behavior will be assessed with the activPAL3 micro accelerometer (PAL Technologies, Glasgow, United Kingdom) for seven consecutive days at

- baseline before the start of the intervention, during three randomly selected weeks over the course of the 3-month intervention, and for one week at both the post-intervention and 3-month follow-up periods. The activPAL provides a valid and reliable measure of posture (sitting/lying vs. standing) for free-living settings and uses a transducer suitable for detecting lower intensity movements. The activPAL will be waterproofed using medical grade adhesive covering and attached to the midline of the thigh using a breathable, hypoallergenic tape. This method allows for the monitor to be worn continuously without removing for bathing or other water-based activities (a valuable feature that reduces missing data).
- Blood pressure will be objectively measured using BpTRU BPM-200 (VSM MedTech Ltd, Coquitlam, Canada), an automated blood pressure recorder that has been validated against the mercury sphygmomanometer. Two blood pressures will be collected and averaged at each data collection time point following a five minute period of rest.
  - Stress will be measured in two different ways: biomarkers of physiological stress using cortisol saliva and perceived stress using questionnaires. Acute stress will be assessed using salivary cortisol levels taken at three different times (upon waking, 30 minutes after waking, and before going to bed) for 2 days at each data collection time point (assayed by UMN ARDL). Participants will be provided detailed instructions. Kits will be sent home with participants with clear instructions for capturing saliva samples in the morning and evening, and storing the date- and time-labeled plastic vials in their home freezer to be carried with them to their next clinic visit. Chronic stress will be assessed using common, valid self-report measures.
  - Additional measures: Trained research staff will collect height, weight, and body fat % using a Shorr Height measuring board and Tanita BF-350 scale, respectively, to calculate BMI. Diet will be assessed using NCI's web-based dietary recall, ASA-24, which has been validated in adults. A self-reported survey will be completed that inquiries on demographic characteristics (age, sex, marital status, education level, income), physical activity-related psychosocial variables (social support, self-efficacy, barriers, enjoyment), eating-related behaviors (intuitive eating, eating as a coping mechanism^72), and additional variables (collectivism, social connectedness, sense of belonging, community cohesion and embodiment). The survey with the listed measures is included with this application.

Post-intervention focus groups to assess intervention feasibility, acceptability, and safety with the overall program and specific components, and in order to inform program improvements will be completed September 2022. The focus group guide is submitted with this IRB application.

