## **17.0 Statistical Considerations**

### 17.1 Data Analysis Plan:

Aims 1-3. Feasibility, acceptability, and safety. Descriptive statistics of survey variables will be compared to the benchmarks in Table 6. For *recruitment*, we will record: a) the count of women

who express interest, b) weeks elapsed to screen 200 women, and c) number enrolled and consented as a % of the targets – 16 for focus groups and 60 for the pilot intervention. For *retention and adherence*, we will compute % of participants who attend  $\geq 80\%$  of the yoga sessions by tracking attendance to all in-person sessions. For *intervention fidelity*, [name] will analyze the videotaped yoga sessions using established criteria to enumerate the number of planned specific yoga components that were completed as a percentage of the total. For *feasibility* we will compute the percentage of participants who: a) receive the materials and resources throughout the intervention, b) rate the assessments as ‘not too burdensome’ on a multiple choice question, and c) complete baseline, post-intervention, and follow-up assessments. For *acceptability* we will compute the percentage of participants who rate the various intervention components as acceptable. For *safety* we will track all adverse events experienced by participants, report them to the UMN IRB, and compare to the benchmarks. If benchmark goals are not met, we will explore why they were not met during the post-intervention focus groups in hopes of gaining substantive information to address the missed benchmark goals in the future trial.

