### **19.0 Confidentiality**

#### 19.1 Data Security:

All data collected, especially participant information, during the study will be treated with strict confidentiality. Information will be entered into our data files by coded numbers (without recording individual names), thus assuring anonymity. Only authorized research staff will have access to participant identities or condition allocation (i.e., [name] and the measurement team will be blind to condition allocation). When the research team reports study results,

participants will not be named or identified in any way. All research team members have (or will) completed human subjects training.

Yoga classes will be recorded as part of the intervention and will be stored on a password-protected, view-only Google Drive. Videos will focus on instructors, with the goal of keeping participants out of the frame. Instructors will sign a video release form and participants will consent to being recorded in case of audio being picked up on the video. Only the research team and participants in the pilot RCT will have access to the catalog of yoga videos. No identifiable information will be shared over the videos.

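### Fidelity is scored only in sessions chosen before delivery and tied to an activPAL request, with no concealment from instructors described, so the 90% benchmark is open to upward observation bias of unknown size

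*Combined protocol and SAP*

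**What the plan says.** Fidelity of delivery is one of the primary feasibility endpoints in section 3.1. The benchmark is that at least 90% "of each videotaped session is delivered as planned based on training".

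Section 5.2 says which sessions are videotaped for this purpose: "One yoga session will be randomly selected biweekly (during weeks 2, 4, 6, 8, 10, and 12) and videotaped so the content can be analyzed". It then adds: "During these videotaped quality control sessions, participants will be asked to wear the activPAL to assess activity intensity".

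Section 17.1 gives the scoring. A member of the team "will analyze the videotaped yoga sessions using established criteria to enumerate the number of planned specific yoga components that were completed as a percentage of" all planned components. No other source of fidelity data is named.

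Section 4.1 sets the schedule: "60-minute yoga sessions will take place three times per week for 12 weeks", delivered "at two intervention locations, 612 Jungle and The Zen Bin".

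Section 19.1, on data security, describes a separate or overlapping set of recordings: "Yoga classes will be recorded as part of the intervention and will be stored on a password-protected, view-only Google Drive". It continues: "Videos will focus on instructors, with the goal of keeping participants out of the frame". Section 20.2 gives the fortnightly quality-control videos two uses: checking that instructors keep to their training, and spotting participants whose poses put them at risk of injury.

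**The concern.** The fidelity endpoint should describe how classes are usually taught, because that is what a later trial needs to know. Random selection within the fortnight stops anyone from choosing a favourable class. It does not stop an instructor from keeping closer to the script once it is apparent that this class has been selected.

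The activPAL request is tied to the scored session, so the selection has to be disclosed to participants by the time the class starts, in a group that the instructor is leading. The person being assessed is therefore well placed to notice. Nothing in the plan scores any other class, so a gap between scored and unscored delivery would not show in the data. A benchmark recorded as met could then fail to describe most of the sessions taught.

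**Working it through.** **There is no figure to reproduce.** The plan gives no sample size, error rate or interval for fidelity. Section 17.1 compares descriptive statistics with the benchmarks.

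**Step 1: when the selection is made.** Participants can be asked to wear a monitor during a particular session only if that session has been identified beforehand. So section 5.2 implies selection before delivery.

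**Step 2: what could reveal the selection.** The documents leave open whether all classes are filmed, so take both cases.
- If only the quality-control sessions are filmed, the camera and the activPAL request both mark the class.
- If every class is filmed, as section 19.1 may intend, the camera singles out nothing, but the activPAL request still does.

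Either way at least one cue remains. It is imperfect, because section 5.2 also has participants wear the activPAL for a full week in three randomly chosen weeks of the intervention.

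**Step 3: coverage.**
- Sessions per series: 3 per week × 12 weeks = 36 (section 4.1).
- Sessions scored: one in each of weeks 2, 4, 6, 8, 10 and 12 = 6 (section 5.2).
- Share scored, single series: 6/36 = 16.7%.
- If each location runs its own series: 2 × 36 = 72 sessions. One draw overall gives 6/72 = 8.3%; one draw per location gives 12/72 = 16.7%. The plan does not say which applies.
- Sessions that can never be drawn: odd weeks, 6 × 3 = 18 of 36, or half. Section 4.1 starts each new theme in an odd week, so the first week of every theme goes unscored.

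**Step 4: how far a visible selection could move the result.** The benchmark applies to each session, so it is met only if all scored sessions reach 90%. If each of six sessions independently reaches 90% with probability p, the chance that all pass is p^6. The values of p are assumptions:

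| p | Chance that all 6 pass |
|---|---|
| 0.60 | 0.05 |
| 0.70 | 0.12 |
| 0.80 | 0.26 |
| 0.90 | 0.53 |
| 0.95 | 0.74 |
| 0.99 | 0.94 |

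For example, if p is 0.80 in an ordinary class and 0.95 in one known to be scored, the chance of meeting the benchmark rises from 0.26 to 0.74. The documents give neither value. If behaviour is the same in both, there is no bias.

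**Step 5: what a perfect result would show even without bias.** If all n scored sessions pass, the exact two-sided 95% lower limit for the share of sessions reaching 90% is 0.025^(1/n). For n = 6 this is 0.54; for n = 12 it is 0.74. This is sampling error under a simple binomial model. It makes no allowance for observation bias or for the odd weeks.

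**The case against.** **The documents do not say that instructors know.** A reader might infer that they are told which class is graded, and hence that the benchmark is biased upward. Neither follows. The plan is silent on notice to instructors and on concealment. Classes are hybrid, so some participants may not be in the room, and nothing says that monitors are fitted in class. This stands: instructors may be able to tell, and the benchmark is open to bias.

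**Filming may not be a cue at all.** If section 19.1 means that every class is recorded, a camera distinguishes nothing. This also stands, but it leaves the session-specific activPAL request. Wear in the three random weeks blurs that cue without removing it, since it is continuous and not tied to one class.

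**A pooled average is not the endpoint.** A reader might assume two delivery percentages, one for scored and one for unscored classes, average them over all classes, and conclude that true fidelity misses 90%. The documents supply no such percentages, and section 3.1 sets the benchmark session by session, so that conclusion is unsupported.

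**The quality-control sessions have other uses.** Section 20.2 relies on those videos to see participants, while the section 19.1 recordings try to keep participants out of frame and cannot replace them. Removing the activPAL would also lose the intensity measure. This limits the remedy: only the fidelity scoring should move.

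**This is a pilot with descriptive benchmarks.** Selection is already random, and instructors are trained and given sequences. That lowers the stakes, but fidelity is still a primary endpoint and the remedy is cheap.

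**Conclusion.** The concern holds as a weakness of method. Fidelity rests only on sessions selected before delivery, a cue tied to those sessions can reveal the selection, no concealment is described, and no other class is scored. The 90% benchmark is therefore open to upward observation bias. The upward direction assumes that instructors who notice keep closer to the plan. The size cannot be estimated, and the bias could be nil.

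What is certain is the narrow base: 6 of 36 sessions, or 6 of 72 if each location runs its own series and one session is drawn overall, with odd weeks excluded. The documents do not show that instructors are told, that the benchmark would be missed in ordinary classes, or that every class is recorded.

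**What to change.** - **Sections 5.2 and 17.1:** draw the sessions scored for fidelity at random after they have been taught, in the same number as now planned, from all twelve weeks and both locations. Score them from the instructor-focused recordings in section 19.1. Tell instructors only that any class may be scored. Any effect of the camera then applies to scored and unscored classes alike.
- **Section 3.1:** make the benchmark refer to the sampled recordings.
- **Section 19.1:** state that every class is recorded and kept at least until fidelity has been scored.
- **Leave in place:** the fortnightly quality-control videos for the safety review in section 20.2, and the activPAL request for activity intensity. Neither should be the sole basis for the fidelity benchmark.

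If sampling after delivery is not adopted, the plan should at least say whether the selection is concealed from instructors and how.

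**Cost:** the number of recordings scored does not rise. Recording and keeping every class becomes a firm requirement, which section 19.1 does not clearly impose now. Measured intensity will no longer always come from the same class as the fidelity score.
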